#### 6.0 Statistical Analysis

The statistical analysis will be conducted using SAS. Summary statistics will be calculated for the overall cohort, as well as by-treatment group. Categorical variables will be presented as frequencies and percentages, and groups will be compared with chi-square or Fisher's Exact tests. Distributions of the continuous variables will be assessed to determine if data transformations or non-parametric tests are needed. Continuous variables will be presented as mean and standard deviation and groups will be compared with ANOVA unless non-parametric tests are warranted, in which case, median and interquartile range will be calculated and Kruskal-Wallis tests will be used to compare groups. For variables with multiple measurements, these statistics will be given for each discrete time point. Myalgia will be assessed as both a categorical variable (any myalgia vs. none), and as an interval variable. A significance level of 5% will be used for all statistical comparisons.

To determine the effect of the treatments over time on the outcomes of interest, mixed models will be utilized, with fixed effects for treatment and time, as well as their interaction, and a random effect for subject. When necessary, additional variables may be added to adjust the models for other noted differences between the treatment groups.

Based on prior observation, the myalgia incident rate is 50%. With 100 patients in each of the three groups, will have 80% power to detect an odds ratio of 2.26 between any two groups, with two-sided tests and an alpha of 0.05 (5% significance level).

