# 2.0 Rationale and Specific Aims

Our hypothesis is that precurarization with rocuronium, followed by a 2 minute interval prior to administering succinylcholine will prevent, or ameliorate, succinylcholine induced myalgias compared to not pretreating, or pretreating with a shorter time interval prior to succinylcholine administration.

Primary endpoint: Does the patient have myalgias post succinylcholine administration with pretreatment with Rocuronium 2 minutes prior?

Secondary endpoint?

\*Severity of myalgias

\*Onset of myalgias postop relative to succinylcholine administration

\*Correlation of myalgias with the presence of skeletal muscle fasciculation upon succinylcholine administration

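### Section 6.0 names no contrast that matches the hypothesis or the powered two-group comparison; read as a three-group chi-square, power at the planned effect is 71–84%, depending on an unstated Group 2 rate

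*Combined protocol and SAP*

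**What the plan says.** Section 2.0 states a directional hypothesis about one arm. Rocuronium given 2 minutes before succinylcholine should prevent or lessen myalgia "compared to not pretreating, or pretreating with a shorter time interval prior to succinylcholine administration". In the notation of Section 4.0 that is Group 3 vs Group 1 and Group 3 vs Group 2, with 100 patients in each of three groups.

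Section 6.0 gives the analysis. For categorical variables: "Categorical variables will be presented as frequencies and percentages, and groups will be compared with chi-square" or Fisher's exact test. For continuous variables it names ANOVA or, where non-parametric methods are warranted, "Kruskal-Wallis tests will be used to compare groups". Myalgia is analysed both as any versus none and as an interval score. A mixed model has treatment, time and their interaction. On error rates: "A significance level of 5% will be used for all statistical comparisons". No pair of groups, contrast, follow-up test or order of testing is named.

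The power sentence in the same section starts from a 50% myalgia rate and claims "80% power to detect an odds ratio of 2.26 between any two groups".

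**The concern.** Hypothesis, power and analysis do not line up. The first two concern pairs of groups. The third, on its natural reading, compares all three groups at once. A three-group chi-square has 2 degrees of freedom and asks whether the three rates differ anywhere.

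Two things are at stake. First, the 80% belongs to a test that the analysis text does not name, and the test it appears to name can have less power when Group 2 lies between the other two. A graded effect of that kind is plausible if a shorter interval gives partial benefit. Second, a significant three-group result may come from Group 2 alone and so would not support the 2-minute hypothesis. If pairs are then compared, their choice and order are left until after the data are seen.

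**Working it through.** **Inputs.** From Section 6.0: Group 1 rate 0.50, odds ratio 2.26, two-sided alpha 0.05. From Section 4.0: n = 100 per arm. The Group 2 rate is not in the documents; it is assumed here to lie anywhere from 30.7% to 50%.

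**Step 1: planned Group 3 rate.** Odds of 1 divided by 2.26 give p = 1/(1 + 2.26) = 0.3067.

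**Step 2: reproduce the 80%.** Two-group test with pooled variance:
- Mean rate = (0.5 + 0.3067)/2 = 0.4034.
- SE under the null = √(2 × 0.4034 × 0.5966/100) = 0.0694.
- SE under the alternative = √((0.25 + 0.3067 × 0.6933)/100) = 0.0680.
- z = (0.1933 − 1.96 × 0.0694)/0.0680 = 0.84, so power = 80.0%.

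Exact enumeration of the uncorrected chi-square gives 80.5%; Fisher's test gives 76.2%. The stated figure is therefore correct for an uncorrected two-group chi-square.

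**Step 3: three-group chi-square at the same effect.** The noncentrality is λ = n Σ(pᵢ − p̄)² / [p̄(1 − p̄)], with 2 df and critical value 5.99.
- Group 2 midway (50/40.3/30.7): λ = 100 × 0.01867/0.2407 = 7.76, power 70.3%.
- Group 2 equal to Group 1 (50/50/30.7): λ = 100 × 0.0249/0.2459 = 10.13, power 82.1%.
- Group 2 equal to Group 3 (50/30.7/30.7): λ = 10.67, power 84.1%.

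Simulation (1,000,000 trials per row), with Groups 1 and 3 at 50% and 30.7%:

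| Group 2 rate (assumed) | Three-group chi-square | Group 3 vs 1 | Group 3 better than both, each at 5% |
|---|---|---|---|
| 50% | 83% | 80.5% | 69% |
| 45% | 74.5% | 80.5% | 50% |
| 40% | 71% | 80.5% | 26% |
| 35% | 76% | 80.5% | 9% |
| 30.7% | 84% | 80.5% | 3% (no true difference from Group 2) |

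The minimum three-group power is 71.1%, at a Group 2 rate of 40.3%; power for both contrasts is 28% there, hence about 27% near 40%. A three-group test followed by Group 3 vs Group 1 only if significant finds that contrast 70–77% of the time.

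**Step 4: which arm.** If only the 2-minute arm works (50/50/30.7), the three-group test is significant in 83% of trials. If only the 1-minute arm works (50/30.7/50), it is also significant in 83%. The p-value does not separate the two cases.

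**Step 5: error rates of pairwise alternatives, all rates 50%.** Chance of at least one false positive:
- All three pairs, each at 5%: 13.5%.
- The two hypothesis contrasts, each at an unadjusted 5%: 10.1%.
- Fixed sequence, Group 3 vs 1 then Group 3 vs 2: the error of the first test alone, nominally 5% (5.6% simulated, because the uncorrected chi-square is slightly liberal here).

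Bonferroni over two contrasts (2.5% each) leaves 71.1% power per contrast and needs 122 per arm to restore 80%. The fixed sequence keeps 80% for the first contrast at 100 per arm. In the 1-minute-only case of Step 4 it claims a Group 3 benefit over Group 1 in 2.8% of trials.

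**The case against.** The strongest objection is that Section 6.0 never says the chi-square is a 3×2 test. The power sentence, with its odds ratio between any two groups and its two-sided tests, suggests that pairwise comparisons may be intended. This stands as a limit on the finding. On that reading the 80% does belong to the intended test. But the phrase occurs only in the power sentence, and the analysis text sets chi-square beside ANOVA and Kruskal-Wallis, which are multi-group tests. If pairs are intended, which pairs, in what order and with what error control remain open (Step 5).

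A reader might infer that the trial has only 71% power, or that the power calculation is wrong. The documents support neither. The 80% reproduces. The 71% needs both the three-group reading and a Group 2 rate near 40%; with Group 2 equal to either other arm, the three-group test has slightly more than 80%.

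A reader might also infer that the plan cannot show the 2-minute arm to be better. That goes too far. Section 6.0 calls for frequencies and percentages by treatment group, so the direction will be visible, and nothing excludes follow-up comparisons or contrasts from the mixed model. What is missing is a pre-specified test of that claim.

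Finally, simply substituting two unadjusted contrasts would raise the false-positive chance to about 10%. That is correct, and it is why the fix orders them. Nor does Section 2.0 clearly require Group 3 to beat both comparators, so power for the joint claim is additional information and not a failed target.

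**Conclusion.** The concern holds as a mismatch between hypothesis, powered comparison and stated analysis. Section 6.0 names neither Group 3 vs Group 1 nor Group 3 vs Group 2. On its natural reading, any myalgia is tested by a three-group chi-square with 71–84% power at the planned effect, against 80% for the test that the power sentence describes, and significance alone does not identify the better arm. The range rests on a 50% control rate, 100 evaluable patients per arm, a Group 2 rate assumed between 30.7% and 50%, and the inferred 3×2 form. The absence of a named contrast does not depend on those assumptions. The data remain fully analysable, so this is a change to make before the analysis and not a flaw in the design.

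**What to change.** In Section 6.0, make the primary analysis of any myalgia a fixed sequence of two uncorrected 2×2 chi-square tests, each at two-sided 5%:
1. Group 3 vs Group 1.
2. Group 3 vs Group 2, only if the first is significant in favour of Group 3.

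Report each odds ratio with a 95% confidence interval. Use the same two contrasts for severity and in the mixed model, and keep the three-group tests as descriptive. The roughly 5% error rate applies to one such sequence; if it is run at both the 3-hour and the 24-hour assessment, the plan must also say which is primary.

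Reword the power sentence. The 80% applies to the single Group 3 vs Group 1 contrast at an odds ratio of 2.26. Power to show Group 3 better than both depends on the Group 2 rate: about 69% if it is 50%, about 27% if it is near 40%.

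Cost: SAP wording and a few lines of SAS, with no extra patients. The second contrast can be claimed only after the first, and the stated power for the joint claim is less favourable than 80%.

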#### 1.0 Background

Since its clinical introduction in the early 1950s, succinylcholine, a short-acting depolarizing muscle relaxant, has become commonly used for rapid sequence intubation during general anesthesia. In addition to its paralytic effects, succinylcholine administration in general anesthesia carries a multitude of risks, among which are muscle fasciculation and postoperative myalgia. Currently, anesthesiologists are divided in whether rocuronium, a nondepolarizing muscle relaxant, effectively reduces both succinylcholine-induced fasciculations and postoperative myalgias in procedures under general anesthesia. There is sparse and inconsistent literature supporting the efficacy of rocuronium pretreatment for the prevention of succinylcholine-induced fasciculations and postoperative myalgias.

Research into managing the side-effects of using succinylcholine first appeared in 1990 when Pace demonstrated, through a meta-analysis of 45 clinical trials, that nondepolarizing muscle relaxants reduced the frequency of postoperative myalgias by 30%. Rocuronium, while not assessed in Pace's study, is now commonly used to prevent fasciculations and myalgias associated with succinylcholine. Motamed, (1998) demonstrated that pretreatment with rocuronium in elective general surgery reduced the incidence of succinylcholine-induced fasciculations. In laparoscopic procedures in female patients under general anesthesia, Martin et. Al (1998), demonstrated that rocuronium prevented fasciculations but not postoperative myalgias. Likewise, Joshi et. Al (1999) showed that rocuronium prevented succinylcholine-induced fasciculations but failed to prevent myalgias in patients undergoing elective ambulatory surgery with general anesthesia..

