# Risks:

There is huge variability in the care of patients receiving succinylcholine in the anesthesia community at large and within our own group. Some people believe that succinylcholine should always be pretreated with a non-depolarizing neuromuscular blocker to prevent myalgias, while others believe that it should never be pretreated because, they believe, that the pretreatment doesn't work and is ineffective. This is a proposal to structure that variability into randomized groups and study the outcomes which will lead to a reduction of said variability going forward. There is no added risk to the patient as there is currently no standardization of the practice within our own group. Pretreating and not pretreating are both practiced daily.

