# 4.0 Enrollment/Randomization

All Endoscopic Retrograde Cholangiopancreatography (ERCP) procedures scheduled at IU Health University Hospital on adult patients (18+ years old) will be identified. Subjects will be contacted face-toface prior to surgery by one of the research team members. They will be informed about the study and all questions will be answered. The potential subjects will be given a copy of the informed consent form and authorization form. The subjects will then be contacted face-to-face in POCU on the day of surgery and if participation is agreed upon, written consent will be taken. All patients will receive general endotracheal anesthesia consistent with acceptable standards of care.

A total of 300 subjects will be randomized by a/ computer program into 3 groups (100 in each group):

- 1. Group 1 (Control): 0 mg/kg of rocuronium pretreatment and 1 mg/kg (rounded up to the nearest 10 mg) succinylcholine
- Group 2: 0.05 mg/kg (rounded up to the next mg) up to 5 mg of rocuronium pretreatment followed by 1.0 mg/kg (rounded up to the next 10mg) succinlycholine t = 1 min +/- 10 sec after pretreatment.
- 3. Group 3: 0.05 mg/kg (rounded up to the next mg) up to 5 mg of rocuronium pretreatment followed by 1.0 mg/kg (rounded up to the next 10 mg) succinlycholine t = 2 min +/- 10 sec after pretreatment.

Drug amount rounding takes into account the limitations to accurately measure drug doses in the clinical setting. Rocuronium is measured in a 1 ml tuberculin syringe with 1mg = 0.1ml. Rounding allows the provider to round to the next 0.1ml. Smaller increments cannot be accurately measured. Likewise, Succinylcholine is 20mg/ml and administered from a pre-labeled, calibrated 10 ml syringe. The above allowable rounding allows the provider to administer the drug to the next nearest 10mg=0.5ml for the same reason.

Randomization will be performed using Research Randomizer in blocks of 30. The primary investigator will inform the person doing the case as to what group the patients are randomized to. Both the patients and the research staff doing assessments will be blinded to the randomization.

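### Does the 80% power for an odds ratio of 2.26 hold between any two groups, or only when one group has a 50% myalgia rate?

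*Combined protocol and SAP*

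**What the plan says.** Section 6.0 (Statistical Analysis) gives one planning rate, "Based on prior observation, the myalgia incident rate is 50" percent, without naming the group it describes. The next sentence is the power statement: "With 100 patients in each of the three groups, will have 80% power to detect an odds ratio of 2.26 between any two groups", for two-sided tests at the 5% level. Section 4.0 (Enrollment/Randomization) confirms equal allocation, "into 3 groups (100 in each group").

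The hypothesis in section 2.0 sets the 2-minute interval against no pretreatment and also against "or pretreating with a shorter time interval prior to succinylcholine administration". Group 3 versus Group 2 is therefore a comparison of interest, alongside Group 3 versus Group 1.

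For categorical outcomes, section 6.0 plans frequencies, percentages and chi-square or Fisher's exact tests. The odds ratio appears only in the power sentence.

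**The concern.** An odds ratio does not define a power for a binary outcome until one of the two rates is fixed. Section 6.0 fixes one rate, 50%, and then appears to extend the result to all three pairs of groups. If the 50% is the rate without pretreatment, and 1-minute pretreatment has some benefit, then Groups 2 and 3 are both below 50%. The comparison of the two intervals would then have less than 80% power at an odds ratio of 2.26.

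The reference group is also open. The Risks section says of local practice: "Pretreating and not pretreating are both practiced daily". The prior observation behind the 50% could thus have come from untreated, pretreated or mixed patients.

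At stake is how a null result for Group 3 versus Group 2 would be read. Someone relying on section 6.0 might credit that comparison with more power than it had.

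**Working it through.** **Inputs.** From section 6.0: 100 per group, a 50% rate, an odds ratio of 2.26, two-sided alpha of 0.05 and a chi-square test. No allowance for dropout is stated and none is used here. Any rate other than 50%, or derived from it through the odds ratio, is an assumption.

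**Formula.** With rates p1 and p2, n per group, mean rate m = (p1 + p2)/2 and difference d = |p1 − p2|:

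power = Φ{ [d − 1.96 × √(2m(1 − m)/n)] / √([p1(1 − p1) + p2(1 − p2)]/n) }

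**Step 1: reproduce the stated figure.** The odds at 50% are 1. Dividing by 2.26 gives 0.4425, a rate of 0.4425/1.4425 = 30.7%. Then d = 0.1933 and m = 0.4034. The two standard errors are 0.0694 (pooled) and 0.0680 (unpooled). Power = Φ[(0.1933 − 1.96 × 0.0694)/0.0680] = Φ(0.842) = 80.0%.

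By symmetry, 69.3% against 50% also gives 80.0%. Solving for the sample size returns 100 per group, and solving for the odds ratio at 80% power returns 2.26. Exact power of the uncorrected chi-square test at 50% against 30.7% is 80.5%. Fisher's exact test, which the plan also allows, has 76.2%.

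**Step 2: hold the odds ratio at 2.26 and move the rates.**

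| Higher rate | Lower rate | Power | n per group for 80% |
|---|---|---|---|
| 60% | 39.9% | 81.6% | 96 |
| 55% | 35.1% | 81.2% | 97 |
| 50% | 30.7% | 80.0% | 100 |
| 45% | 26.6% | 78.0% | 106 |
| 40% | 22.8% | 75.0% | 113 |
| 35% | 19.2% | 71.1% | 124 |
| 30.7% | 16.4% | 66.7% | 137 |

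Power is slightly above 80% when the two rates lie either side of 50%. It falls when both are below 50%, and also when both are above it: 75% against 57.0% gives 76.9%, and 80% against 63.9% gives 72.0%.

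**Step 3: what the documents say about Group 2.** They give no expected rate. Section 1.0 cites a meta-analysis reporting that "nondepolarizing muscle relaxants reduced the frequency of postoperative myalgias by 30" percent. By the plan's own account that analysis did not assess rocuronium, and the text does not say whether the reduction is relative or absolute. Read as relative, 50% × (1 − 0.30) = 35%, which is the 71.1% row. The same section says: "There is sparse and inconsistent literature supporting the efficacy of rocuronium pretreatment", and it describes trials in which rocuronium prevented fasciculations but not myalgia. A Group 2 rate still at 50%, with the full 80% power, is equally compatible with the text.

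**Step 4: hold the absolute difference at 19.3 points instead.**

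| Higher rate | Lower rate | Power |
|---|---|---|
| 50% | 30.7% | 80.0% |
| 45% | 25.7% | 82.1% |
| 40% | 20.7% | 85.0% |
| 35% | 15.7% | 88.7% |
| 30.7% | 11.3% | 92.4% |

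The direction reverses. Whether Group 3 versus Group 2 is weaker or stronger than the headline comparison depends on the effect scale, and the plan does not fix one for the analysis.

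**The case for a change.** The strongest case for a change is that the wording is unconditional while the 80% is conditional, and that this is so whatever Group 2's rate turns out to be. If only the control group is at 50% and both pretreated groups improve on it, the pair left outside the claim is one the hypothesis names. The plan itself chose the odds ratio to express its power, so the statement ought to be right on that scale. Naming the 50% group and stating the rates would take one sentence and alter no procedure.

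The algebra in this stands: the 80% does depend on the rates, and the reference group is unnamed. What does not stand is the step from there to a defect. The condition is printed in the sentence before the claim. The phrase about any two groups is naturally read as saying that the calculation is pairwise with equal group sizes. The remark on daily practice does not show where the 50% came from. If it is a mixed average with the two groups' rates on either side of it, power is slightly above 80%.

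**Conclusion.** No change is needed. Section 6.0 is numerically correct under the rate it states: 80.0% power for 50% against 30.7% (or 69.3%) with 100 per group, two-sided 5%, uncorrected chi-square test and no dropout.

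On the odds-ratio scale the possible overstatement for Group 3 versus Group 2 is 2 points if Group 2 is at 45%, and about 13 points (80.0 − 66.7 = 13.3) if it is at 30.7%. It is nil if Group 2 is at 50%. All of these rest on assumed Group 2 rates. For a fixed 19.3-point difference there is no shortfall at any of them. The documents therefore do not show that the comparison of the two intervals is underpowered.

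The sample size, tests and conclusions would be the same with or without more exact wording. An analyst would report that comparison with its estimate and confidence interval, and these convey its precision better than the planning sentence can. Stating which group the 50% describes is a courtesy to the reader, not a correction.

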# 7.0 Reporting of Adverse Events or Unanticipated Problems Involving Risk to Participants or Others

Adverse events, other than those measured as end points, should be reported to the principal investigator, [name] at **[contact].** 

# 8.0 Study Withdrawal/Discontinuation

Participants may withdraw at any time.

# 9.0 Privacy/Confidentiality Issues

Participant privacy is an important goal of the researchers. Only members of the research team will have access to identifiable data. All study papers containing patient identifiers will be kept in each subjects confidential study file accessible to only the research team. All records will be kept in a locked room in a locked cabinet that only authorized staff enters. Collected data from each enrolled participant will be recorded on Redcap which is a secure web-based data collection tool. Quality assurance steps of testing Redcap will be completed by the study team prior to moving it into production mode. Quality control methods of randomly doing double checks of data entered for accuracy will be complete as well as extraction and cleaning of data for data analysis every 1 year. All electronic information and paperwork containing patient identifiers will be deleted or shredded when data analysis is completed and the paperwork is no longer needed, or for 7 years per Indiana law.\_

# 10.0 Follow-Up and Record Retention

Follow-up myalgia assessments will be performed at 3 hour and 24 hours after surgery.

The patient data related to the study will be entered into a secure REDCap database. Paper copies of study data will be kept in the locked anesthesiology offices. Following completion of the study, all copies of data collected will be stored for the required amount of time (min. 7 years) and then will be physically destroyed.

